-Testing hypothesized differences between experimental and control groups will use an intent-to-treat analysis that includes all participants randomized. LGM will examine the effect of treatment condition on trajectories of change separately for each of the outcomes over the one-year follow-up. To test Hypothesis 1, we will assess the trajectories of the mothers' outcomes (mental health, physical health, substance abuse, etc.) and predict of the trajectory of change by intervention condition (Healthy Home vs. TAU). Controlling for the effects of socio-demographic variables and pretest levels of the dependent variables is possible in LGM, if these variables are found to differ by randomization group. To test Hypothesis 2, a similar procedure will consider children's outcomes (mental health, physical health, behavior problems, etc.).

- Testing mechanisms of action. Using Mplus 6, this set of analyses will investigate links between trajectories of change (growth curves) for the hypothesized mechanism of action variables (mediators) and trajectories of mothers' outcomes or children's outcomes following MacKinnon, Lockwood, Hoffman, West and Sheets' (2002) procedures. This method is more powerful than the classic (Baron & Kenny, 1986) method, particularly for binary outcomes. LGM can also test multiple indirect paths or mediators (i.e., Hypothesis 3c) with this method.

- Clinically significant change procedures (Jacobson & Traux, 1991) can also investigate efficacy of an intervention. These procedures: 1) determining whether participants have made statistically reliable change and 2) categorizing subjects according to clinically meaningful cut-points, e.g., recovered (statistically reliable change that moves a client out of clinical range), improved (statistically reliable improvement, but still in the clinical range), and unimproved/deteriorated.

-Implementation analysis will be used to determine the feasibility of adapting Healthy Home for other agencies. Using cost logs for training and service delivery, the total cost of

implementing Healthy Home can be determined. Therapist and agency satisfaction as well as therapist fidelity to Healthy Home will be assessed to determine if changes to the Healthy Home implementation protocol are needed.

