-Mothers will have additional data from baseline assessments administered by the treatment agency: a GAIN-I administered at treatment intake and a GAIN-M90 administered 90 days into treatment. As noted in the measures section, several variables (e.g., demographics, history of abuse) will be taken from the GAIN-I. There are a number of follow-up analyses that may provide greater understanding of the direct and interactive relationships between symptoms, intervention, and post-treatment substance use, including adding to growth models of mental or physical health and examining moderators of treatment effects. [The GAIN is no longer being used in the study]

- Proposed moderators will be used in two types of analyses. The variables might predict trajectories of change of the mothers' and children's outcomes, only. For example, does poor sleep contribute to early relapse for mothers in recovery? The moderators might also interact with treatment. For example, do mothers from different ethnic groups respond differently to Healthy Home? Effect sizes will be generated for future intervention development/refinement from the results of these exploratory analyses.

- Secondary data analysis will be used to examine data extracted from clinical intervention forms related to health assessments, recommendations/referrals, treatment/services rendered, follow-up plan of care, and education provided to individuals during home health visits.

- Missing data and attrition patterns will be examined. In research with samples of individuals in substance use recovery some loss to follow-up is expected. Our proposed methods allow the inclusion of cases with randomly missing data, we will test for non-randomness, i.e., a non-ignorable or informative missing data pattern (Little & Rubin, 1987). If there is differential attrition by condition, alternative models will be examined (in addition to the proposed) which account for or model the attrition mechanism (Angrist, 1997; Heckman, 1979; Idson & Feaster, 1990) to produce a more robust range of estimates.

Privacy/Confidentiality Agreements

4.13. **Describe any privacy agreements or certificates of confidentiality, if applicable.**
We have received a certificate of confidentiality from NIH.

4d. Description of Study (cont'd)

Deception

4.14. *** Is the use of deception part of the study design?**

Yes No

If yes, please answer the following 3 questions:

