We have received a certificate of confidentiality.

5b. Inclusions/Exclusions

5.4. * Is the population being enrolled in this study at high risk for incarceration?

Yes No

5.4.A. If yes, will the subjects be withdrawn from the study once they are incarcerated?

Yes No

5.4.A.(i) If the above answer (question 5.4.A.) is no, describe how re-contacting/re-consenting, treatment, and/or follow-up will occur:

We will not conduct study procedures with participants while they are incarcerated but will not withdraw them from the study as they may be available to conduct study procedures upon release if they are still within the study timepoint windows. If a mother is incarcerated we will attempt to conduct follow-up assessments within the appropriate timepoint windows with children enrolled in the study if they can be accompanied by an adult family member.

NOTE: If a subject becomes incarcerated while enrolled in a study, all research interactions and interventions with that subject, and the obtaining of identifiable private information about the subject, must cease until the requirements of subpart C have been satisfied with respect to the relevant protocol.

If notified that a previously enrolled research subject has become a prisoner, the principal investigator must promptly seek IRB re-review of the protocol in accordance with the requirements of subpart C if the principal investigator wishes to have the prisoner-subject continue to participate in the research. In special circumstances in which the principal investigator asserts that it is in the best interests of the subject to remain in the research study while incarcerated, the IRB Chairperson may determine that the subject may continue to participate in the research until the requirements of subpart C are satisfied.

5.5. * What are the criteria for exclusion of participants from the research?

Persons who do not meet the inclusion criteria listed below will be excluded.

5.6. * Will any population be systematically excluded in this study?

Yes No

5.6.A. If yes, provide rationale/justification for this exclusion:

5.7. * What are the criteria for inclusion of participants in the research?

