6.2.A. Please upload copies of scripts, recruiting materials, and advertisements:

Name	Description	Version
20111132_ADV_IRBApp_HealthyHomeFlyer_ENG		0.04
20111132_ADV_IRBApp_HealthyHomeFlyer_SPA		0.03
20111132_ADV_IRBApp_HHBrochure_ENG		0.05
20111132_ADV_IRBApp_HHBrochure_SPA		0.04
ChildID_translation.doc		0.02
Healthy Home Tear Off Flyer English.docx		0.03
Healthy Home Tear Off Flyer Spanish.docx		0.03
Mother's Screening Form_translation.doc		0.02
Treatment assignment Postcard with Translation.docx		0.01

NOTE: Any materials that will be given to or seen by potential subjects must be reviewed and approved by the IRB. This includes assessments, instruments, diaries, questionnaires, and all screening and recruitment materials, including advertisements, web postings, letters, and telephone scripts. Only IRB approved versions of these materials may be used during the course of the study.

6.3. * What measures will be taken during the recruitment process to safeguard against the potential coercion or the appearance of coercion of participants, particularly vulnerable populations?

Study candidates will be told (verbally and in writing) that their participation is voluntary, that they may withdraw consent at any time, and that their decisions regarding participation will not affect their relationship with Banyan.

6.4. * Are there specific criteria to prematurely end a particular subject's participation in the study (e.g., predetermined safety endpoints, unexpected clinically significant

findings, distress or serious adverse events, etc.)?

Select one

- Yes
- No
- Not Applicable

6.4.A. If yes, please describe:

6.5. * Will subjects be remunerated for their participation in the study in any way other than credit toward a course requirement?

- Yes No

6b. Remuneration

6.5.A. * List type, frequency, interval, and total value of remuneration:

Type of Remuneration	Frequency	Total Value
View Cash	4	Mothers will be paid \$50 per assessment interview. Mothers will receive a \$20 bonus if all of her enrolled children attend.

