View Gift Certificates	4	Children will receive a \$10 (age 10-12) or \$20 (age 13-17) gift card. Mothers will receive a giftcard with a value of \$20. to encourage participation in the first intervention visit. Those mothers who are assigned to the Healthy Home condition will receive the gift card at their first home visit. Those who are assigned to TAU will receive the gift card at their next follow up assessment. For participants who enrolled in the study before the gift card procedure was approved, those in Healthy Home who have already been terminated from the intervention will receive the gift card at their next assessment.

6.5.B. * If a subject withdraws from the study early, will remuneration be prorated?

yes

6.5.B.(i) If yes, describe plan for prorating payments and ensure that this plan is defined in consent forms:

Participants will be remunerated for assessments that they attend and complete.

6.5.B.(ii) If no, justify why prorated payment is not being offered:

6c. Financial Liability

6.6. * Financial Liability for Study Participants:

Complete the table below, indicating the responsible party for payment of research activities and procedures.

Not applicable

Procedure or Activity	Frequency
There are no items to display	

6.7. * Select all categories indicating costs which participants or their insurance companies will be responsible for:

Check all that apply

- Participants will have no costs associated with this study
- Study-related procedures which would be done under standard care
- Study-related procedures not associated with standard care
- Administration of drugs/devices
- Study drugs
- Study devices

Other

6.7.A. If other, please specify:

The study does not cover costs to participants for the outpatient substance abuse treatment (they are already enrolled in substance abuse treatment when they enroll in the study) or costs associated with referrals made by the Healthy Home nurse.

6.8. * In the event of study-related subject injury, who will be responsible for compensation?

Not Applicable

6.8.A. If Other 3rd Party, please specify:

7. Informed Consent

7.1. * Is an alteration of the consent process being requested?

Yes No

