7.10. **Consent may be required from a parent, legal guardian, legal representative, court-appointed representative, or health care surrogate where research involves children/minors, wards of the state, cognitively or developmentally impaired individuals, comatose or traumatized or emergency subjects, as well as any other subjects lacking capacity to consent. Such surrogate/representative/guardian can only consent if the IRB has approved the research under HHS or FDA regulations. For court-appointed guardians, court assent is required.**

If your study involves any of these groups, please specify below whether consent will be obtained from such surrogate/representative/guardian and describe the process for obtaining such consent:

Mothers will be asked to provide permission for their childrens' participation. In cases where a person other than the mother has legal custody of the child, that person will be asked for signed permission. If there are wards of the state, the court-appointed designee would have to provide legally effective consent. Children age 7 or above will have the study explained and asked to give assent when they attend the baseline appointment.

- 7.11. *** What protections will be offered to persons with cognitive impairment or to persons determined to be incapacitated? Describe how capacity for consent will be determined, whether cognitive capacity is expected to change significantly during the study, whether a legally authorized representative or health surrogate has been designated for purposes of obtaining informed consent, and whether court approval has been obtained (for court-appointed guardians). Describe plans to re-consent subjects after a change in the subject's cognitive capacity.**

Not applicable

- 7.12. *** How will informed assent for children and parental consent/permission be obtained?**

Not applicable

Mothers will be asked to provide permission for their childrens' participation. In cases where a person other than the mother has legal custody of the child, that person will be asked for signed permission. Children age 7 or above will have the study explained and asked to give assent when they attend the baseline appointment.

- 7.13. *** Describe plans to re-assent or obtain consent for child subjects during the study if the subject reaches the age of majority (18 years) or if there is a significant change in cognitive capacity (i.e. gets older or regains consciousness).**

Not applicable

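### The main child-effect growth models use no maternal follow-up data, so child visits missed because of the mother's relapse or absence would modestly understate the child effect

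*Combined protocol and SAP*

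**What the plan says.** **Analysis (4.12).** Treatment effects on trajectories are modelled "separately for each of the outcomes over the one-year follow-up", and Hypothesis 2 (children) follows a procedure like that for the mothers. The adjustment variables mentioned are socio-demographics and pretest levels, and only if they differ by arm. No maternal follow-up variable is named for the Hypothesis 2 models, either as covariate or as auxiliary. On missing data, the plan states: "Our proposed methods allow the inclusion of cases with randomly missing data". It adds a test for non-randomness. Models of the attrition mechanism follow only if attrition differs by condition.

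**Child attendance.** 6.5.A pays the mother $50 per interview and a $20 "bonus if all of her enrolled children attend". Children aged 10 to 12 get a $10 card, and the older group a $20 card ("age 13-17) gift card"). None is listed for ages 2 to 9, although 5.7 enrols from age 2. 6.5.B(i) adds: "Participants will be remunerated for assessments that they attend and complete".

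**When the mother is not available.** 5.4.A.(i): "If a mother is incarcerated we will attempt to conduct follow-up assessments within the appropriate timepoint windows with children enrolled in the study", provided an adult relative comes with them. 7.10 and 7.12 foresee cases where "a person other than the mother has legal custody of the child", and 5.7 requires only monthly contact between mother and child. 6.5.A lists no payment to that relative or custodian.

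**The concern.** Several child measures need the child to be present: the Youth Self-Report, the child-report scales, and height and weight. Whether the child comes depends on the mother's circumstances. Her relapse is an Aim 1 outcome, and family functioning is an Aim 3 mechanism.

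A likelihood-based growth model handles missing data without bias when missingness depends only on what is in the model. If a child is missed because the mother relapsed, and relapse also worsens the child's outcome, her status must be in the likelihood for that to hold. In a child-only model it is not. If Healthy Home lowers relapse, more of the badly affected children drop out of the TAU data, and the observed arm difference shrinks. Aim 2 would then understate the benefit that passes through the mother's recovery.

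**Working it through.** **No figure to reproduce.** The plan gives about 172 mothers, with no power calculation, allocation ratio or dropout rate. What follows is illustration, and every rate in it is assumed.

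**Inputs.** Mother relapsed or unavailable: p = 0.40 in TAU, 0.25 in Healthy Home. Child attendance: 0.85 when the mother is well, and a = 0.75, 0.60 or 0.45 when she is not. The child outcome is 0.5 SD worse after maternal relapse, and treatment acts on the child only by that route. There are 172/2 = 86 mothers per arm (1:1 assumed), with one child each.

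**True effect.** 0.5 × (0.40 − 0.25) = 0.075 SD.

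**Observed effect.** Among attending children, the share whose mother relapsed is p·a / [p·a + (1 − p)·0.85]. The observed effect is 0.5 × the difference in that share.

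| a | Share, TAU | Share, Healthy Home | Difference (true 0.150) | Attenuation | Observed effect | Bias |
|---|---|---|---|---|---|---|
| 0.75 | 0.370 | 0.227 | 0.143 | 4.6% | 0.072 SD | 0.003 SD |
| 0.60 | 0.320 | 0.190 | 0.130 | 13.7% | 0.065 SD | 0.010 SD |
| 0.45 | 0.261 | 0.150 | 0.111 | 26.1% | 0.055 SD | 0.020 SD |

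**Would the attrition trigger fire?** The missing proportion is 1 − [p·a + (1 − p)·0.85]. The plan does not say how differential attrition is judged. A two-sided 5% test of two proportions is assumed.

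| a | Missing, TAU | Missing, Healthy Home | Power, 86 per arm |
|---|---|---|---|
| 0.75 | 19.0% | 17.5% | 6% |
| 0.60 | 25.0% | 21.3% | 9% |
| 0.45 | 31.0% | 25.0% | 14% |

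**Wider range.** Take 10% missing when the mother is well and 30% to 70% when she is not, relapse of 40% vs 25% or 50% vs 30%, and a relapse effect of 0.3 to 0.8 SD. The bias then runs from 0.004 to 0.060 SD and the trigger's power from about 8% to 38%. With equal relapse in both arms the bias is zero.

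**Scale.** The standard error of a two-arm difference is about √(2/86) = 0.15 SD. The main illustration's largest bias is 0.020/0.15 = 0.13 standard errors. The wider range's largest is 0.060/0.15 = 0.4.

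**Why maternal data help.** If missingness depends only on maternal relapse, the mean among attending children within each relapse group is unbiased. Weighting those means by the full p in each arm returns 0.5 × 0.15 = 0.075 SD. This needs relapse to be recorded when the child is absent.

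**The case against.** The case against is substantial.

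- **The bonus is an addition, not a barrier.** It comes on top of $50 per interview, and the documents give no attrition figure. A reader might infer that the all-children condition makes child data go missing. Nothing in the documents shows that, and the calculation above does not model the bonus. Paying per attending child instead would be a trade-off, since it weakens the reason to bring the last child.
- **The plan already supports attendance.** Children aged 10 to 17 have their own cards, home assessments are offered, mothers may be assessed by phone, staff call monthly, and the final window extends to 18 months. Jailed mothers are not withdrawn.
- **Some child data do not need the child.** The instruments in 4.4.A include mother-report versions of the child health and dental measures.
- **Maternal variables are not absent from every child model.** The mediator models link mechanism variables to children's trajectories, and moderators such as the mother's stress may predict them. A reader who infers that no child model holds maternal information goes too far. But those are separate or exploratory analyses, and they do not estimate the main Hypothesis 2 effect.
- **The closed form overstates somewhat.** It uses one wave of observed cases. The growth model also uses the child's baseline and earlier waves, which carry part of the signal.
- **Auxiliaries do little when mother and child are lost together.**

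These points limit the size and remove the payment rule as a cause. They leave two gaps standing: the Hypothesis 2 models name no maternal follow-up variable, and the plan states no action on non-random missingness unless attrition differs by arm.

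**Conclusion.** The point holds as a modest missing-data weakness in 4.12. If child-attended measures are missed more often when the mother has relapsed or is unavailable, and Healthy Home reduces relapse, the child effect that runs through her recovery is biased toward zero. On the main assumed inputs this is about 5% to 26% of that path, or 0.003 to 0.020 SD. Harsher inputs reach 0.060 SD. Either is well below one standard error, so the bias alone would seldom change the conclusion on Aim 2. The reason to act is that the relevant data are largely planned already and the attrition trigger would usually stay silent.

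The trigger is aimed at the right thing, since in this illustration bias and unequal attrition arise together. It simply has little power at this sample size. The result rests on assumed relapse and attendance rates, 1:1 allocation, and one child per mother.

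The silence of 6.5.A on paying an accompanying adult is a minor side point. That item asks about payment to subjects, and the consent forms, which are not in the copy reviewed, may say more.

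**What to change.** 1. **In 4.12**, add to every Hypothesis 2 child growth model, at each wave, the mother's substance use (ASI-Lite and urine screen), her assessment attendance, and household or contact status (Household Composition Form). Enter them as auxiliary missing-data variables, not as adjustment covariates: they are measured after randomisation and lie on the hypothesised causal path, so adjusting for them would remove part of the effect. Where the outcome model is not normal, multiple imputation with the same variables serves the purpose.
2. **Also in 4.12**, pre-specify a sensitivity analysis for non-random missingness in the child outcomes, run whether or not attrition differs by arm. This covers families in which mother and child are lost together.
3. **Optional, 6.5.A**: allow the existing $20 bonus to be paid to the adult relative or custodian who brings the children when the mother cannot.

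**Cost.** Item 1 needs a few lines of model code and a check that the Household Composition Form is completed at every wave, which the plan does not state. Urine results will be missing for mothers assessed by phone. Item 2 is analysis time only. Item 3 costs at most $20 per family visit and a short IRB amendment.
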